8.2.5 Hematological test (from the start of the first anticancer chemotherapy)

Target : Analysis set

[figure not shown]
population

n

Endpoint : red blood cell count ($\times 10^4/\mu\text{L}$)
 hemoglobin (g/dL)
 hematocrit (%)
 white blood cell count (/ μL)
 neutrophil count (/ μL)
 eosinophil (%)
 basophil (%)
 monocyte (%)
 lymphocyte count (/ μL)
 platelet count ($\times 10^4/\mu\text{L}$)
 CRP (mg/dL)
 total protein (g/dL)
 albumin (g/dL)
 AST (IU/L)
 ALT (IU/L)
 LDH (U/L)
 BUN (mg/dL)
 creatinine (mg/dL)
 Na (mEq/L)
 K (mEq/L)
 Cl (mEq/L)
 NLR

Statistical analysis : Summary statistics of end points will be calculated by each timing of evaluation (At the start of first line chemotherapy/ immediately before the first avelumab administration/ at the start of fourth cycle of avelumab treatment/ at the time of PD judgment (at the latest test during the observation period for those continuing avelumab

treatment without disease progression).

The figure consists of two vertically stacked bar charts. The top chart has 12 horizontal bars of varying lengths. The bottom chart has 15 horizontal bars, with the first bar in each row being light gray and the subsequent bars being black.

A horizontal bar chart consisting of two sets of 20 bars each, positioned side-by-side. The bars are rendered in black and have varying widths. The chart is set against a white background with no grid lines. The bars on the left side are generally longer than those on the right side, with the longest bar on the right side reaching approximately two-thirds of the way up the chart area. The bars are separated by small gaps.

六

CC1

CCI

11 References

- Pre-pembrolizumab neutrophil-to-lymphocyte ratio (NLR) predicts the efficacy of second-line pembrolizumab treatment in urothelial cancer regardless of the pre-chemo NLR
Cancer Immunol Immunother. 2022 Feb;71(2):461-471. doi: 10.1007/s00262-021-03000-8. Epub 2021 Jul 7.

12 Revision record

Version	Date of creation	Reason for revision
Version 1.0	2 November 2022 EPSCo., Ltd. [name]	New document
Version 1.1	21 December 2022 EPSCo., Ltd. [name]	Correction of typographical errors Addition of determination rules for tumor histological type Addition of the starting dose of corticosteroid

End of document

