9. RESEARCH METHODS

9.1. Study design

This study is a multicenter, non-interventional, retrospective, medical chart review of locally advanced or metastatic UC patients who were prescribed avelumab as 1L maintenance therapy between 24 February 2021 and 30 November 2021 in Japan. All decisions regarding clinical management and treatment of the participating patients were made by the investigator as part of standard care in a real-world clinical setting and were not contingent upon the patient's participation in the study. Data will be collected if available per study site.

- Index date: The date of first prescription for avelumab between 24 February 2021 (launch date of avelumab) and 30 November 2021
- Observation period: Patients will be followed from index date to 30 Jun 2022

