9.2.2. Secondary endpoints

Efficacy endpoint

- Time to treatment failure (TTF) of avelumab

Definition of TTF is provided in 20. The following avelumab treatment data will be collected:

- 1) Date of start and end of avelumab administration
- 2) Dosage of avelumab
- 3) Date of avelumab discontinuation and interruption
- 4) Reason for avelumab discontinuation and interruption
- 5) Date of last survival confirmation

- Real-world progression-free survival (rwPFS)

Definition of rwPFS is provided in 20. The following data will be collected:

- 1) Date of start of avelumab treatment (administration)
- 2) Date of first disease progression or death due to any cause, whichever came first
- 3) Date of last survival confirmation

- Objective Response Rate (ORR)

ORR is defined in 21. The following data will be collected:

- 1) Tumor assessment (CR, PR, SD, PD)

- rwPFS from chemotherapy (rwPFS-c)

Definition of rwPFS-c is provided in Section 9.2.3.4. The following data will be collected:

- 1) Date of start of 1L Cht (administration)

- 2) Date of first disease progression or death due to any cause during avelumab treatment, whichever came first
- 3) Date of last survival confirmation

Safety endpoints

- Corticosteroid therapy for immune-related adverse events (irAEs)
The following data will be collected:
 - 1) Date of treatment
 - 2) Drug name of corticosteroid
 - 3) Starting dose of corticosteroid
 - 4) Duration of corticosteroid treatment
- Premedication for potential infusion-related reaction of avelumab
The following data will be collected:
 - 1) Presence of premedication for infusion-related reaction of avelumab
 - 2) Drug name used for premedication for infusion-related reactions of avelumab
- Treatment for infusion-related reaction of avelumab
The following data will be collected:
 - 1) Presence of treatment for infusion-related reaction of avelumab
 - 2) Drug name used for treatment for infusion-related reaction of avelumab
- Regimen after avelumab maintenance therapy
The following data will be collected:
 - 1) Medication for UC after avelumab maintenance therapy (drug name, start date of treatment, end date of treatment)
- Hematological test (after the start of 1L Cht)
The following data will be collected:
 - 1) Red blood cell count/ hemoglobin/ hematocrit/ white blood cell count (neutrophils, eosinophils, basophils, monocytes, lymphocytes)/ platelet count/ C-reactive protein (CRP)/ total protein/ albumin/ AST/ ALT/ LDH/ BUN/ creatinine/ Na/ K/ Cl

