Data collection scope: At the start of 1L cht / immediately before the first avelumab administration/ at the start of fourth cycle of avelumab treatment/ at the time of PD judgment (at the latest test during the observation period for those continuing avelumab treatment without disease progression)

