5.2 Handling of missing values

An absence of data for analysis will be treated as missing values, and no special imputation processing will be performed using statistical methods.

However, if there are specifications for handling of missing values in subsequent each specification, they are followed.

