5.5 Derived variable

The items and definitions of variables whose derivation is necessary at the time of statistical analysis are shown below.

Continuous variable

Item	Derivation method
Treatment-free interval: Time from the end date of first-line chemotherapy to the start date of avelumab administration (days)	Start date of initial administration with avelumab – end date of first-line chemotherapy administration + 1
Duration of treatment of first-line chemotherapy (days)	End date of first-line chemotherapy administration – start date of first-line chemotherapy administration + 1
Duration of treatment (irAE treatment) of corticosteroid (days)	End date of corticosteroid administration – start date of corticosteroid administration + 1
Time to treatment failure of avelumab (TTF)	Defined as the period from the date of start of avelumab to the date of end of treatment* for any reasons including death. If there is no record of end of treatment, patients will be censored at the date of last observation during the study period. *The following sensitivity analysis will also be performed. Considering its clinical meaning, "interruption due to being well-controlled" does not correspond to "treatment failure"; it should be treated as an event on the day when the death or discontinuation was observed prior to the last observation date. If no death or discontinuation occurred before the date of the last observation, data will be censored at the date of the last observation.
Real-world progression-free survival (rwPFS)	Defined as the period from the start date of avelumab maintenance therapy to the date of first

	
disease progression (clinical evaluation based on imaging examinations, laboratory tests, and pathological tests, as well as other evaluations by the investigators of each institution) or death from any cause, whichever occurs earlier.
 
If there is no record of death or disease progression, patients on second or later lines (following avelumab maintenance therapy) will be censored at the start of the second-line treatment, and patients on only avelumab maintenance therapy will be censored at the date of the last visit during the study, based on the medical record.

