6.3 Details of statistical analysis

6.3.1 Summary statistics

If summary statistics is described in this plan, the following values will be calculated unless otherwise specified.

Number of subjects, number of subjects with missing, mean, standard deviation, minimum value, quartile point (25% point, 50% point [median], 75% point), maximum value

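### The fourth laboratory timing pools values at progression with latest values of progression-free patients, and assigns no value to those who stopped avelumab without recorded progression

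*SAP*

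**What the plan says.** Protocol 9.2.2 lists a haematological test among the safety endpoints, with four collection points: start of first-line chemotherapy, immediately before the first avelumab dose, start of the fourth avelumab cycle, and "at the time of PD judgment (at the latest test during the observation period for those continuing avelumab treatment without disease progression". SAP 4.2 repeats this rule, and so does SAP 8.2.5: "at the time of PD judgment (at the latest test during the observation period for those continuing avelumab", again limited to those without progression.

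For the analysis, SAP 8.2.5 states: "Summary statistics of end points will be calculated by each timing of evaluation". It gives no breakdown by progression or treatment status.

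On gaps in the data, SAP 5.2 says that "no special imputation processing will be performed using statistical methods". SAP 6.3.1 defines each summary as starting with "Number of subjects, number of subjects with missing, mean, standard deviation", so a missing count is shown but not its cause.

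The protocol also collects the "Reason for avelumab discontinuation and interruption" (9.2.2, under time to treatment failure).

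**The concern.** The fourth timing is one column filled from two sources. One is a value taken when the disease is judged to have progressed. The other is the most recent value in a patient who is still on avelumab and has not progressed. Markers such as LDH, CRP or NLR could plausibly differ between these states. A single mean then depends on the share of patients who happened to progress, and a shift from the earlier columns cannot be assigned to progression or to continued treatment.

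The rule also names only two groups. A patient who stopped avelumab with no progression on record belongs to neither. Because the test is listed under safety, a reader will want to know how many such patients there are and why they stopped. A bare missing count does not say.

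**Working it through.** **1. The rule in its three places.** Protocol 9.2.2, SAP 4.2 and SAP 8.2.5 agree on the fourth timing, so the pooling is planned and is not a slip in one document.

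**2. Where each kind of patient falls under the rule.**

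| Status by 30 June 2022 | Value at the fourth timing |
|---|---|
| Progression judged while on avelumab | At progression |
| Stopped avelumab, progression judged later | At progression, but off avelumab |
| Continuing avelumab, no progression | Latest test |
| Avelumab interrupted, no progression | Not stated whether this counts as continuing |
| Stopped avelumab or died, no progression recorded | None assigned |

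The plan expects patients in the last two rows. The reason for stopping or interrupting is collected. SAP 5.5 has a sensitivity analysis for "interruption due to being well-controlled". The rwPFS definition in Protocol 9.2.3.2 has a censoring rule for patients who start the next line with neither progression nor death recorded. With no imputation, a patient in the last row can enter only the missing count.

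**3. Time on study.** Protocol 9.1 states: "Patients will be followed from index date to 30 Jun 2022". Protocol section 6 gives a minimum follow-up of 7 months. By the SAP 5.3 rule (target date − start date + 1, with 30 days to a month):

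- Last index date, 30 November 2021: 212 + 1 = 213 days; 213 / 30 = 7.1 months. This agrees with the stated minimum.
- First index date, 24 February 2021: 491 + 1 = 492 days; 492 / 30 = 16.4 months.

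A continuing patient's latest test can therefore fall as late as 7.1 to 16.4 months after index, depending on the index date. A value at progression can fall at any time after index. The column mixes times on treatment as well as disease states.

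**4. Effect of pooling (illustration).** Let w be the share of contributors at progression and g the difference between the group means, in units of a common within-group SD. Neither is in the documents; both are assumed.

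- Pooled mean = w × (mean at progression) + (1 − w) × (mean of continuing patients)
- Distance from the progression mean = (1 − w) × g
- Distance from the continuing mean = w × g
- Pooled SD = √(1 + w(1 − w)g²)

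| w | g | From progression mean | From continuing mean | Pooled SD |
|---|---|---|---|---|
| 0.3 | 0.5 | 0.35 | 0.15 | 1.03 |
| 0.3 | 1.0 | 0.70 | 0.30 | 1.10 |
| 0.5 | 0.5 | 0.25 | 0.25 | 1.03 |
| 0.5 | 1.0 | 0.50 | 0.50 | 1.12 |
| 0.7 | 0.5 | 0.15 | 0.35 | 1.03 |
| 0.7 | 1.0 | 0.30 | 0.70 | 1.10 |

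Over these ranges the pooled mean lies 0.15 to 0.70 SD from each group's own mean.

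**The case against.** The strongest reply is that this is one column of a descriptive table. No objective in Protocol 8.2 concerns laboratory toxicity, SAP 8.2.5 plans no test, and the count of missing values is disclosed. All of that is true and limits the weight of the point. It does not make the pooled column readable, and a missing count without a cause does not tell the reader who is absent.

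Several stronger readings are tempting, and the documents do not support them.

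- *The whole laboratory summary lacks a defined state.* The other three timings are each a single defined point.
- *Everyone who stopped for toxicity is left out.* The progression rule is not limited to progression on treatment, so a patient who stopped and progressed later can enter. Patients who stopped early still count at both pre-avelumab timings, and at cycle 4 if they reached it. Corticosteroid use and infusion-reaction treatment (SAP 8.2.1 to 8.2.3) are analysed in the full analysis set.
- *No within-patient change is planned anywhere.* SAP 5.5 defines an NLR shift from the start of chemotherapy to the start of avelumab, and the SAP is redacted after 8.2.5. One can say only that the readable 8.2.5 states no change scores.
- *A further laboratory timing should be collected for those who stopped.* That would mean a full panel outside the scope in Protocol 9.2.2. Data collection was planned to end on 30 November 2022, before SAP version 1.1 of 21 December 2022.

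**Conclusion.** The point holds for the fourth timing only. Its pooled statistics describe neither patients at progression nor patients on continuing treatment, and patients who stopped with no progression on record have no assigned value and no stated explanation. Whether interrupted patients count as continuing is left open.

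The numerical size is unknown. The 0.15 to 0.70 SD range rests wholly on the assumed shares and differences, and the documents give no count of patients who stopped without progression. The conclusion also assumes that the redacted text after SAP 8.2.5 holds no split by status; the readable text of 8.2.5 has none. This is a worthwhile improvement in reporting at little cost, and no primary result or hypothesis test is affected.

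**What to change.** In SAP 8.2.5:

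1. Summarise the fourth timing separately for (a) patients at the judgment of progression and (b) patients continuing avelumab without progression, using their latest test.
2. State whether a patient on interruption counts as continuing.
3. Beside these columns, report the number who stopped avelumab without recorded progression, by the recorded reason.
4. Optionally, give the within-patient change from the pre-avelumab value at cycle 4 and in each final group, for patients with both values.

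The progression dates, avelumab dates, reasons for stopping and pre-avelumab values are already within the scope of Protocol 9.2.2, so no new data collection is needed. The cost is SAP wording, a few more table columns and smaller numbers in each group.
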